7.1.6. SCD-Related Complications

7.1.6.1. Vaso-Occlusive Crisis (VOC)

VOC must be documented in the participant's medical record that the participant was seen by, or in contact with the Investigator or health care provider. The event may take place in a medical setting (hospital, clinic, emergency room) or at home.

Acute chest syndrome (ACS) is defined as an acute illness characterized by fever and/or respiratory symptoms, accompanied by a new pulmonary infiltrate on a chest X-ray.

VOC during the treatment period is defined as:

A composite of acute painful crisis or ACS, and includes the following:

- Moderate to severe pain lasting at least 2 hours
- No explanation other than VOC
- Requires oral or parenteral opioids, ketorolac, or other analgesics prescribed or directed by a healthcare professional
- May include episodes of ACS

VOC events and associated therapies will be summarized via descriptive statistics. These endpoints include:

- Rate of VOC during treatment with voxelotor
- Rate of VOC hospitalization during treatment with voxelotor
- Rate of RBC transfusion during treatment with voxelotor
- Rate of opioid use during treatment with voxelotor

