8. BIOSTATISTICS

8.1. Statistical Methods

Statistical programming and analyses will be performed using established statistical methods. Details of all planned analyses will be specified in a separate statistical analysis plan (SAP).

The study data will be reported using summary tables, figures, and data listings. Continuous variables will be summarized using mean, standard deviation (SD), median, minimum, and maximum. Categorical variables will be summarized by presenting the number (frequency) and percentage in each category.

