#### 2. INTRODUCTION

The objective of Study GBT440-034 (C5341022) is to assess the long-term safety and treatment effect of voxelotor in participants with sickle cell disease (SCD) who have completed treatment in Study GBT440-031.

This statistical analysis plan (SAP) provides details of the planned analyses and statistical methods for Study GBT440-034 final clinical study report (CSR). Where this document differs from the high-level analysis plan described in the study protocol, the methodology described in this SAP is considered the latest and supersedes the corresponding section(s) in the protocol.

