## **5.4.2.** Vaso-occlusive Crisis (VOCs)

Vaso-occlusive crises (VOCs) are as defined in protocol Section 7.1.6.1 and are a composite of acute painful crisis and acute chest syndrome events. The annualized incidence rate of ontreatment VOC events will be calculated and 95% confidence interval provided. VOC events with an onset date from informed consent to last dose date will be included in the summary.

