#### 5.4.3. Therapies Associated with Sickle Cell Disease

The incidence rate and reasons for on-treatment red blood cell (RBC) transfusions will be summarized. RBC transfusions with an onset date from informed consent to last dose date will be included in the summary.

Opioid usage will be identified based on reported concomitant medications. The number and percentage of participants reporting opioid use at baseline and post-baseline will be summarized.

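### The SAP plans no analysis of the VOC hospitalization rate that the protocol lists as an endpoint, and does not say it was dropped

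*Protocol*

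**What the plan says.** Protocol 7.1.6.1 introduces its list with "VOC events and associated therapies will be summarized via descriptive statistics. These endpoints include" and then names four rates during treatment: VOC, VOC hospitalization, RBC transfusion and opioid use. The second reads "Rate of VOC hospitalization during treatment with voxelotor". The same section defines a VOC without regard to setting: "The event may take place in a medical setting (hospital, clinic, emergency room) or at home". Protocol 8.1 leaves the detail of every planned analysis to the SAP.

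SAP 5.4.2 takes its VOC definition from protocol 7.1.6.1 and plans one summary: "The annualized incidence rate of ontreatment VOC events will be calculated and 95% confidence interval provided". It counts events with onset from informed consent to last dose. SAP 5.4.3 covers the two therapies: "The incidence rate and reasons for on-treatment red blood cell (RBC) transfusions will be summarized", and for opioids "The number and percentage of participants reporting opioid use at baseline and post-baseline will be summarized".

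SAP section 2 states that, where the two documents differ, "the methodology described in this SAP is considered the latest and supersedes the corresponding section(s) in the protocol".

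**The concern.** SAP 5.4.2 relies on the protocol section that lists the hospitalization rate, yet carries over only the pooled VOC rate. VOC hospitalization does not appear in the SAP's endpoints (2.2), its adverse event tables (5.3.2) or its section on SCD-related complications (5.4). A programmer working from the SAP would not produce it, and the study report would lack a result that the protocol promised.

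The pooled and hospitalized rates answer different questions. One counts all qualifying crises and the other counts those that led to admission. They could move differently over long follow-up, and the pooled rate alone would not show it.

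**Working it through.** No arithmetic applies. Neither document states a VOC hospitalization rate, an event count or a precision target, so the check is a comparison of text.

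**Step 1. Map the four items of protocol 7.1.6.1 to the SAP.**

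| Protocol item | SAP analysis | Status |
|---|---|---|
| VOC rate | 5.4.2: annualized rate with 95% interval | Present |
| VOC hospitalization rate | None | Absent |
| RBC transfusion rate | 5.4.3: incidence rate and reasons | Present |
| Opioid use rate | 5.4.3: number and percentage of participants | Present, but not as a rate |

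**Step 2. Can the pooled VOC rate stand in?** No. It includes events managed at home, in clinics and in emergency rooms. The SAP plans no split by setting, so the hospitalized part cannot be recovered from it.

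**Step 3. Can the serious adverse event output stand in?** SAP 5.3.2 plans tables of SCD-related treatment-emergent SAEs overall, by study year and by relatedness, and a listing of SAEs. Crisis and acute chest syndrome are in that group. Five differences prevent it from giving the endpoint:

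- *Seriousness.* Inpatient hospitalization is one of six seriousness outcomes in protocol 7.2.1.1.
- *Event types.* The SCD-related group also contains pneumonia, priapism and osteonecrosis.
- *Measure.* No annualized rate is planned for SAEs. SAP 5.4 gives annualized rates only for complications (5.4.1) and VOCs (5.4.2).
- *Window.* Treatment-emergent events run to 28 days after last dose (SAP 3.1), while VOCs stop at last dose (SAP 5.4.2).
- *Recording.* Protocol 7.2.2.5 has SCD complications entered as an AE or SAE only when the investigator judges them worse or changed in nature. A crisis in line with the participant's usual pattern might lead to admission without becoming an SAE record.

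**Step 4. Does the acute chest syndrome rate stand in?** No. SAP 5.4.1 plans it, but it covers one component of the VOC composite and does not address admissions for painful crisis.

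**Step 5. Is the interval method ready to borrow?** SAP 5.4.2 promises a 95% interval without naming a method or a denominator. SAP 5.4.1 names both: exact Poisson limits and total assessment time. An added rate should therefore cite 5.4.1.

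**The case against.** The strongest case on the other side is that the item has modest standing. It appears only in protocol 7.1.6.1. The synopsis, the endpoint section (3.1.1) and the statistics section (8.1.1.2) do not name it, and every analysis is descriptive. Table mock-ups are in a separate document that is not available here, and protocol 8.6 allows departures from the SAP to be explained in an updated SAP or the study report. Related data will be visible in the SAE tables and listings. All of this limits the consequence. It does not remove the gap: protocol 7.1.6.1 calls the item an endpoint, and SAP section 6 describes the mock-ups as supporting analyses proposed in the SAP, where this one is absent.

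Three stronger readings are tempting, and the documents do not support them.

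- *That this is the VOC measure least open to open-label bias.* The documents do not rank the measures. Protocol 7.1.6.1 requires every VOC, including one at home, to be documented in the medical record with contact with the investigator or a health care provider. Admission is itself decided with treatment known. Acute chest syndrome, which requires a new infiltrate on X-ray, is arguably at least as objective, and its rate is planned.
- *That the SAP has overruled the protocol here.* The precedence clause applies where the documents differ. On this item the SAP is silent, so removal and oversight cannot be told apart.
- *That the information is lost altogether.* It is partly visible in the SAE output, though not as the endpoint that the protocol names.

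**Conclusion.** The point stands as an unreconciled omission. One of the four items listed in protocol 7.1.6.1 has no analysis in the SAP, no stated reason for its absence, and no substitute among the planned outputs. It should be settled before the final analysis.

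Its size cannot be put as a number. The documents give no person-time and no hospitalized event count for this study, and an interval computed from assumed values would show only that a rate can be estimated, not what its omission costs. The consequence is one missing descriptive result, with no effect on any test, sample size or decision rule.

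The conclusion rests on the SAP text as supplied. If the mock-ups already contain a VOC hospitalization table, the SAP text still needs to define it.

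**What to change.** Add to SAP 5.4.2 an annualized rate of on-treatment VOC events with inpatient hospitalization, overall and by prior treatment group, specifying:

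- **Events:** VOCs as defined in protocol 7.1.6.1 that involve inpatient hospitalization, with onset from informed consent to last dose, as for all VOCs.
- **Person-time:** the sum over participants of (last dose date − informed consent date + 1) / 365.25, which matches the event window.
- **Rate and interval:** total events divided by total person-years, with the exact Poisson 95% limits of SAP 5.4.1. State the same denominator and method for the pooled VOC rate, since 5.4.2 gives neither. These limits do not allow for repeat events within a participant and may be too narrow, which a footnote can say.
- **Data source:** either the VOC record or the hospitalization seriousness criterion. Because of protocol 7.2.2.5, confirm first that the chosen source captures all admissions for VOC. The documents do not describe a case report form field for this.

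If the endpoint was dropped on purpose, record the removal and the reason in the SAP instead.

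The cost is a short SAP paragraph, one table row and the check on capture. If admissions prove to be incompletely recorded, report the rate with that limitation stated.

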7.1.7. Other SCD-related Complications

SCD-related complications will be collected and assessed over the duration of the study.

7.2. Adverse and Serious Adverse Events

Safety assessments will consist of recording all AEs and SAEs, protocol-specified hematology and clinical chemistry variables, clinical examination findings, measurement of protocol-specified vital signs, and the results from other protocol-specified tests that are deemed critical to the safety evaluation of voxelotor.

All AEs will be recorded from the time the study participant signs the ICF until at least 28 days after last dose of study drug or EOS visit (per Appendix 1). The determination, evaluation, reporting, and follow-up of AEs will be performed as outlined in this section. At each visit, the study participant will be asked about any new or ongoing AE since the previous visit. Assessments of AEs will occur at each study visit.

Clinically significant changes from study baseline in physical examination findings, weight, vital signs, and clinical laboratory parameters, will be recorded as AEs or SAEs, as appropriate.

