15. APPENDICES

Appendix 1. Schedule of assessments

Assessments			Tre	eatment I	Period					End of Studyi
Study Day(s)	Day 1ª	W4* ± 5 days	W8* ± 5 days	W12 ± 5 days	W24 ± 10 days	W36 ± 10 days	W48 ± 10 days	Q12 Wks ± 10 days	Q24 Wks ± 10 days	
Informed Consent/Assent	X							unjs	unjs	
Eligibility Assessment	X									
Medical History	X									
Physical Examination b	X	X	X	X	X		X		X	X
Vital Signs ^c	X	X	X	X	X		X			X
Adverse Events	X	X	X	X	X		X		X	X
Concomitant Medications	X	X	X	X	X		X		X	X
Hematology/Chemistry analyzed by Central Laboratory (US and Europe only) ^d	X	X	X	X	X		X			X
Hematology/Chemistry analyzed by Local Laboratory (ex-US and ex-Europe only) ^{d, e}	Xª	X	X	X	X		X		X f	Х
Exploratory Laboratory CCI (US and Europe Only)	X			X	X		X			
Urine Pregnancy Test ^g	X	X	X	X	X		X		X	X
Drug Dispensing and Accountability ^h	X			X	X	X	X	X	X	Х

Assessments		Treatment Period							End of Studyi	
Study Day(s)	Day	W4*	W8*	W12	W24	W36	W48	Q12	Q24	
	1ª	± 5	± 5	± 5	± 10	± 10	± 10	Wks	Wks	
		days	days	days	days	days	days	± 10	± 10	
								days	days	

Amendment 3

Abbreviations: Q = every; W = week; Wks = weeks

- * Participants from GBT440-031 who received GBT440 900 mg or placebo, or who received voxelotor for less than 12 weeks will have additional assessments at Week 4 and Week 8.
- a. Eligibility assessments will be determined on Day 1 prior to dosing. If labs were done for GBT440-031 or this study within 7 days of Day 1, they do not need to be repeated on Day 1.
- Abbreviated Physical Exam which includes: general appearance, examination of eyes, skin, cardiovascular and respiratory systems, an abdominal examination and a symptom directed examination.
- c. Vital signs (heart rate [HR], blood pressure [BP]) will be collected after a participant has rested for at least 5 minutes in the seated or supine position. A repeated measurement of HR and BP will be taken if the first reading is outside the normal range and deemed clinically significant.
- d. Hematology assessments will include: red blood cell (RBC), hematocrit (Hct), hemoglobin (Hb), platelets, white blood cell (WBC), we reticulocytes, absolute reticulocytes, RBC distribution width (RDW), mean corpuscular volume (MCV) and mean corpuscular hemoglobin concentration (MCHC). After Week 48, hematology assessments should only be performed per standard of care.

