- e. Serum chemistries will include: Alanine aminotransferase (ALT), alkaline phosphatase (ALK), aspartate aminotransferase (AST), bicarbonate, BUN, creatinine, LDH, sodium, potassium, bilirubin (total, direct, and indirect). After Week 48, serum chemistries should only be performed per standard of care.
- f. After Week 48 (for participants enrolled outside of the United States and Europe), laboratory values for measures of hemolysis such as hemoglobin, % reticulocytes, absolute reticulocytes, and bilirubin (total, direct, and indirect) will be collected every 24 weeks.
- g. If a urine pregnancy test is positive, the result must be confirmed per local standard of care (eg. ultrasound or serum pregnancy test).
- h. Voxelotor will be dispensed in 12-week (~90 day) intervals with instruction to participants to return any used/unused bottles to clinic.
- The End of Study (EOS) visit should be conducted within 28-35 days after last dose of study drug for participants who withdraw from the study early.

The EOS visit can occur any time after participants obtains commercial voxelotor for participants who complete study per protocol. Participants who complete study per protocol should remain on study drug until EOS visit is completed.

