# 2.1. Study Design

Study GBT440-034 is a multicenter, global, open-label extension (OLE) study available to participants who were previously enrolled and treated in Study GBT440-031. Participants must meet the entry criteria for this study to be eligible for enrollment.

All participants enrolled in GBT440-034, regardless of treatment received in the parent study GBT440-031 (i.e., placebo, voxelotor 900 mg, or voxelotor 1500 mg), receive treatment with voxelotor 1500 mg once daily (the highest dose deemed safe for continued assessment based on GBT440-031).

All participants in Study GBT440-034 have scheduled study visits with assessments at Day 1, Week 12, Week 24, and Week 48, and then every 24 weeks thereafter. Participants who were treated with placebo or voxelotor 900 mg in Study GBT440-031 have additional study visits with assessments at Week 4 and Week 8.

Participants may receive voxelotor in GBT440-034 as long as they continue to receive clinical benefit which outweighs risk as determined by the Investigator and/or until the participant has access to voxelotor from an alternative source (i.e., commercialization or through a managed access program).

Additional details and background information are provided in the study protocol.

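### Protocol 7.2 calls for AE assessment at each study visit, but Appendix 1 schedules none at the dispensing-only visits, so the AE interval after Week 24 is 24 weeks instead of 12

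*Protocol*

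**What the plan says.** Protocol 7.2 sets AE enquiry by visit: "At each visit, the study participant will be asked about any new or ongoing AE since the previous visit", followed by "Assessments of AEs will occur at each study visit".

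The schedule in Protocol Appendix 1 is narrower. Its Adverse Events row is marked at Day 1, Weeks 4, 8, 12, 24 and 48, every 24 weeks, and End of Study. It is blank at Week 36 and in the every-12-weeks column. The Concomitant Medications row has the same pattern. The row "Drug Dispensing and Accountability" is marked in both of those columns, and footnote h adds: "Voxelotor will be dispensed in 12-week (~90 day) intervals with instruction to participants to return any used/unused bottles to clinic". Protocol 5.2 refers to these occasions as dispensation visits.

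Two places side with the schedule. Protocol 7.1 names AE monitoring and concomitant medication use among the safety measures and refers to Appendix 1 for their timing. SAP 2.1 says that participants "have scheduled study visits with assessments at Day 1, Week 12, Week 24, and Week 48, and then every 24 weeks thereafter", and so lists neither Week 36 nor the 12-weekly occasions.

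**The concern.** A site that works from Section 7.2 asks about AEs every 12 weeks. A site that works from Appendix 1 hands over the next supply without asking, and after Week 24 asks every 24 weeks. The protocol does not say which governs.

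This matters because the AE row is the scheduled collection point for much of what the study reports. Appendix 1 has no separate row for vaso-occlusive crises or other complications of sickle cell disease, and SAP 5.4.1 takes complication rates from treatment-emergent AEs. A crisis need not bring the participant to the study site: "The event may take place in a medical setting (hospital, clinic, emergency room) or at home". After Week 48 vital signs are no longer scheduled until End of Study. Laboratory tests revert to standard of care, apart from haemoglobin and haemolysis measures outside the US and Europe. The AE interview is then a main source of safety data, in the long-term period that the study was set up to describe.

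The interval also lengthens partway through follow-up. Fewer non-serious events reported in later years could then partly reflect less frequent asking.

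**Working it through.** The plan gives no figure to reproduce. The check sets the schedule rows against the text and computes the resulting intervals.

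**Step 1. The rows.** Each row in Appendix 1 has ten cells for ten columns, so the blanks are not an artefact of a broken table.

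| Row | D1 | W4 | W8 | W12 | W24 | W36 | W48 | every 12 wk | every 24 wk | EOS |
|---|---|---|---|---|---|---|---|---|---|---|
| Adverse Events | X | X | X | X | X | – | X | – | X | X |
| Concomitant Medications | X | X | X | X | X | – | X | – | X | X |
| Dispensing | X | – | – | X | X | X | X | X | X | X |

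Weeks 4 and 8 apply only to participants who previously received placebo or 900 mg, or who had less than 12 weeks of treatment.

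**Step 2. Intervals.** For all participants the scheduled AE checks fall at Weeks 0, 12, 24, 48, 72 and so on. The gaps are 12, 12, 24, 24, ... weeks, while the dispensing gap stays at 12.

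- Gap after Week 24, current schedule: 24 × 7 = 168 days. With ±10 days at each end, at most 168 + 20 = 188 days (26.9 weeks).
- Gap after Week 24, if Week 36 and the every-12-weeks column were marked: 12 × 7 = 84 days, at most 84 + 20 = 104 days (14.9 weeks).

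**Step 3. How much follow-up is affected.** For a participant followed H weeks, the share of follow-up inside a 24-week gap is (H − 24)/H.

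| H (weeks) | Share in 24-week gaps | Visits after Week 24 without an AE check |
|---|---|---|
| 48 | 24/48 = 50% | 1 of 2 |
| 96 | 72/96 = 75% | 3 of 6 |
| 144 | 120/144 = 83% | 5 of 10 |
| 192 | 168/192 = 87.5% | 7 of 14 |

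These horizons are illustrative; SAP Table 1 lists windows to Week 192 and continues. Over four years (208 weeks) the visits after Week 24 run from Week 36 to Week 204, which is 15. Seven have an AE check (Weeks 48, 72, 96, 120, 144, 168, 192) and 8 do not.

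**Step 4. Which outputs see the change.**

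- SAP 5.3.2 tabulates TEAEs and treatment-emergent SAEs by study year. SAP 3.1 defines study year as study day divided by 365.25, rounded up, so Year 1 is Days 1 to 365. If consent and first dose fall on the same day, about 168 of those 365 days (46%) lie in gaps of 12 weeks or less and the rest in 24-week gaps. Every later year lies wholly in 24-week gaps.
- SAP 5.4.1 and 5.4.2 give complication and crisis rates over the whole period, with no breakdown by year.
- SAP 5.4.3 gives opioid use as the number and percentage of participants at baseline and post-baseline.

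**The case against.** The strongest reply is that the dispensing-only occasions are deliberate. Physical examination, vital signs, AEs, medications and pregnancy test are all blank there, Protocol 7.1 defers to Appendix 1, and SAP 2.1 counts only the other visits. Protocol 7.1.3 and 7.1.5.4 also say all visits for items that are blank in these columns, which suggests that visit may have meant assessment visit. This reading is plausible, but no passage exempts the dispensing occasions. They have their own columns with windows, and Section 5.2 calls them visits. The SAP governs the analysis and cannot settle what sites do. Even on this reading the 24-week interval remains.

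The reply is right on several consequences that a reader might infer:

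- **Home crises forgotten over 24 weeks.** Protocol 7.1.6.1 requires documented contact with the investigator or a health care provider, so a qualifying crisis should have a record. What remains is that the provider may be outside the study site, which then learns of the event late or not at all.
- **Crisis or complication rates showing a false time trend.** The SAP plans no such rates by year.
- **Distorted opioid and transfusion results.** A yes/no opioid summary is much less sensitive to the interval than a rate would be, and transfusions are medical procedures that are hard to forget.
- **Missed SAEs.** Protocol 7.2.3 requires reporting within 24 hours of site knowledge, whatever the visit schedule. This limits the problem but does not remove it, because the clock starts only when the site knows.
- **Sites already differing.** The conflict makes this possible; the documents do not show it.
- **A contradiction on concomitant medications.** Section 7.2 speaks only of AEs, and Section 5.5.1 sets no visit frequency. No text conflicts with the schedule on that row.

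Finally, a change now would be late. Amendment 3 dates from December 2023 and the SAP is written for the final report. New checks would apply only from implementation and would themselves change ascertainment.

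**Conclusion.** The text and the schedule conflict on AE assessment and must be reconciled. Under the schedule, the AE interval after Week 24 is 168 days (at most 188) instead of 84 (at most 104), and about half of the later visits pass without an AE enquiry. The main effect is later or less complete capture of non-serious AEs, and of crises treated away from the study site, between 24-weekly visits. How many events are lost cannot be derived from the documents.

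In the planned outputs the shift matters for the TEAE and SAE tables by study year, as a comparison of Year 1 (mixed 4-, 12- and 24-week intervals) with later years (uniformly 24 weeks). Years 2 onward share one schedule, so a general warning against reading any year-to-year change would go too far.

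The conclusion assumes that participants attend the clinic for dispensing. This is inferred from the wording of Section 5.2 and the return of bottles to clinic; no home-delivery route is described.

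**What to change.** **Preferred.** In Appendix 1, mark Adverse Events at Week 36 and in the every-12-weeks column, to match Section 7.2. Mark Concomitant Medications there too, as an inexpensive improvement and not as the correction of a contradiction. Add these occasions to SAP 2.1. Record the date of implementation so that the change in ascertainment can be seen in the data.

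**If the sponsor keeps the schedule.** Correct Section 7.2 to say that dispensing-only visits carry no AE assessment. State in the SAP that the AE recall interval lengthens from 12 weeks or less to 24 weeks after Week 24, so that differences in TEAEs between Year 1 and later years are not read as a treatment time trend. Under the preferred route the same sentence is worth including for data collected before the change.

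**Cost.** Changing Appendix 1 needs a protocol amendment with IRB/EC approval before implementation (Protocol 11.1), at approximately 100 planned sites, plus a short interview at visits already scheduled. It adds no visit or procedure. Keeping the schedule costs a corrected sentence in the protocol, through the same amendment process, and a sentence in the SAP.
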